8.3 Methods for assessing primary and secondary endpoints

1. Clinical assessment of study participants for the presence of symptoms of respiratory infection

- 2. Laboratory diagnostics of the presence of SARS-CoV-2: swab PCR test;
- 3. Chest computed tomography, pulse oximetry to assess the severity of the disease;

4. Laboratory diagnostics of SARS-CoV-2 infection: plasma IgG;

5. Laboratory diagnostics of the severity of COVID-19: clinical blood test with leukocyte count, C-reactive protein, D-dimer, ALT, AST, bilirubin fraction; creatinine, urea, protein fractions; amylase; glucose;

6. The need for oxygen support and its type in the treatment of COVID-19; the duration of the need for oxygen therapy; duration of mechanical ventilation.

7. Working hours (hours) with patients with confirmed / suspected SARS-CoV-2 infection;

8. Additional observation of all study participants up to 8 weeks from the date of randomization.

Methodology for calculating the time of work with SARS-CoV-2 infection

1. Units of time calculation - hours;

2. Separately taken into account: a) the time of work in the therapeutic department, including the emergency room where patients with suspected / confirmed SARS-CoV-2 infection are located; b) the time of work in the intensive care unit, where patients with suspected / confirmed SARS-CoV-2 infection are located; c) the time of work in a "clean" area, outside the presence of patients with suspected / confirmed SARS-CoV-2 infection;

3. Working hours in the hospital without personal protective equipment in accordance with the regulations of Almazov National Medical Research Centre.

9. Randomization and sample size estimation

Randomization method: 1:1, allocation by minimization method to the preventive therapy group with Bromhexine hydrochloride and to the control group, taking into account the following factors: age (ranges 18-45, 45-64, 65-74, 75-79); type of contact with SARS-CoV-2 infection: ("red zone"; "green" zone); taking hydroxychloroquine to prevent COVID-19.

• "Red" zone: the closest and longest contact with SARS-CoV-2 infection associated with an infected aerosol (work in intensive care units and intensive care units; in operating and intervention laboratories; work with biological material of infected patients);

• Green Zone: work outside direct contact with patients with confirmed / suspected SARS-CoV-2 infection.

Known statistics:

• The incidence rate of medical personnel working with SARS-CoV-2 infection: ranges between 20 and 50% (https://www.cdc.gov/mmwr/volumes/69/wr/mm6915e6.htm?deliveryName=USCDC_425-DM25898);

• Frequency of serious side effects of bromhexine hydrochloride: no more than 0.16 cases per million patients (Ambroxol and bromhexine containing medicinal products. EMA / PRAC / 800767/2015, 10/09/2015);

Estimated effect of preventive therapy:

Empirically, it is suggested that prophylactic drug administration can reduce the incidence of the primary endpoint by 20%.

Calculation of the study sample size:

• Power: 80%

• Confidence level - alpha error: 5%

• The incidence of the primary endpoint in the control group is estimated 30%; the incidence of the primary endpoint in the study group is estimated 10%;

• Thus, the target sample size: 118 people (59 subjects in each group)

• Estimated dropout rate from study protocol (dropout after randomization, non-SARS-CoV-2 incidence) 15%; thus, the required number of participants in the study will be 139 people;

10. Bromhexine hydrochloride dosing and administration rules

The drug is administered orally, after meals, without chewing, with plenty of liquid: 3 times a day, 8 mg.

In case of impaired renal function (creatinine clearance <30 ml / min / 1.73 m2) and / or liver insufficiency (an increase in the level of hepatic transaminases by 2 or more times), the drug should be discontinued in this study.

11. Study timeline

Evaluations	0	7 days	14 days	21 days	28 days	5-8 weeks		
Test (PCR) SARS- CoV-2	+	+	+	+	+	+		
Enzyme immunoassay - IgG to SARS- CoV-2	+*							
Clinical follow-up, daily	+	+	+	+	+	+		
Bromhexine hydrochloride administration, daily (8 mg 3 times a day)	+	+	+	+	+	+		
Individual protective equipment; daily	+	+	+	+	+	+		
Concomitant pharmacological treatment record	+	+	+	+	+	+		
Participant's questionnaire maintaining	+	+	+	+	+	+		
Laboratory diagnostics when SARS-CoV-2 is expected			When indicated					
Chest computed tomography when SARS-CoV-2 infection is expected				When indica	ted			

Table 1. Schedule of evaluations and prophylactic measures

*Plasma biobanking with subsequent IgG analysis when it is possible

12. Subject exclusion

Participants in the study can leave at any time, for any reason, without any consequences. A participant might be excluded from the study for a medical emergency.

Study participant specific withdrawal criteria:

• The presence of side effects of the use of Bromhexine hydrochloride, which complicates its further safe use and / or any other intolerance to the drug;

- The onset of pregnancy;
- Suspected / confirmed SARS-CoV-2 infection;
- Period of disability and / or hospitalization associated with SARS-CoV-2 infection.

13. Replacement of subjects when excluded from the study

Participants excluded from the study will not be replaced.

14. Preliminary study termination

The study may be terminated prematurely if there is a significant difference in the safety endpoints between groups after enrollment of 20 subjects, which indicates unacceptable safety. If the superiority of the treatment method is found early, there will be no reason for early termination of the study.

15. Safety reports

15.1 Adverse events (AE).

Adverse event is any unwanted event that may occur to a study subject during the study course, whether or not associated with bromhexine hydrochloride treatment. All adverse events reported by an investigator should be recorded.

Examples of adverse events based on studies in patients taking bromhexine:

Significant: allergic reaction in the form of anaphylactic shock;

Minor: nausea, vomiting, diarrhea, allergic reaction in the form of urticaria

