Camostat on reducing the severity of the incidence of COVID19: The Effect of Camostat Mesylate on COVID-19 Infection in Ambulatory Patients: An Investigator-Initiated Randomized, Placebo-Controlled, Phase IIa Trial, clinicaltrials.gov: NCT04353284, sample of 114 patients, study start date 04/30/2020 (Yale University, USA); The Impact of Camostat Mesilate on COVID-19 Infection: An Investigator-initiated Randomized, Placebo-controlled, Phase IIa Trial; clinicaltrials.gov: NCT04321096, sample of 180 patients, study start date - 03/31/2020 (Dani me, 9 participating centers).

We suggest, that when SARS-CoV-2 has already entered the cells, the effect of Bromhexine hydrochloride therapy will be low or insufficient. About 20-30% of medical personnel are infected with SARS-Cov-2. At the same time, there are similar data on the potential effectiveness of Bromhexine hydrochloride in the prevention of a new infection in risk groups from several independent groups of authors. According to data from personal communication with specialists in Germany, there were no cases of infection among those who took the drug prophylactically [Department of Anesthesiology, Intensive Care, Pain Management and Palliative Care, Marienkrankenhaus, Soest, Germany]. It can be assumed that there is a preventive effect of taking Bromhexine among medical personnel to reduce the risk of infection and COVID 19 disease, despite the use of personal protective equipment.

2. Purpose

To evaluate the efficacy and safety of oral administration of Bromhexine hydrochloride for the prevention of SARS-CoV-2 infection and COVID-19 disease in medical personnel managing patients with COVID-19

3. Study type

Prospective randomized open-label study with a control group, which assesses the superiority of prophylactic therapy

4. Inclusion criteria

- 1. Age \geq 18 years;
- 2. Negative test (PCR) for SARS-CoV-2 infection;
- 3. Absence of clinical manifestations of a respiratory infection;
- 4. Presumptive management of patients with laboratory and/or clinically confirmed COVID-19;
- 5. Signed informed consent to participate in the study.

5. Exclusion criteria

- 1. Intolerance to Bromhexine hydrochloride;
- 2. Work outside of contact with SARS-CoV-2 infection;
- 3. Pregnancy (positive laboratory test for pregnancy or ultrasound confirmation of pregnancy) and breastfeeding period;
- 4. Other circumstances that the researcher considers inappropriate to participate in this study.

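### Hydroxychloroquine prophylaxis is balanced at allocation, but the plan neither carries it into the primary comparison nor uses its own drug record to show whether use diverged between the open-label arms

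*Combined protocol and SAP*

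**What the plan says.** Section 3 describes a "Prospective randomized open-label study with a control group, which assesses the superiority of prophylactic therapy". No placebo is described, so participants, who are medical staff, know their arm.

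Section 9 specifies "Randomization method: 1:1, allocation by minimization method" on three factors: age band, contact zone and "taking hydroxychloroquine to prevent COVID-19". This is the only mention of hydroxychloroquine in the documents.

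Table 1 in section 11 has a row "Concomitant pharmacological treatment record", marked at every time point from day 0 to weeks 5-8. No section states what the record is for.

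The eligibility criteria (sections 4 and 5), drop-out criteria (section 6), dosing rules (section 10) and withdrawal criteria (section 12) do not mention hydroxychloroquine or any other prophylaxis. Neither the text nor the contents list has a statistical analysis section, so no method is given for the primary comparison and no minimisation factor is assigned a place in it.

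The primary endpoint (section 8.1) combines a positive PCR with clinically suspected COVID-19.

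**The concern.** By minimising on hydroxychloroquine, the plan treats it as something that may be related to infection risk. Two consequences are then left open.

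First, a factor used in allocation should also appear in the analysis. If it is prognostic and is ignored, the unadjusted test is conservative: its standard error still includes variation between factor levels that the allocation has removed from the difference between arms.

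Second, minimisation acts once, at entry. Staff who know that they have no study prophylaxis might start hydroxychloroquine more often than those on bromhexine, or the reverse might happen. Either way the contrast would no longer be bromhexine against no bromhexine on an equal background. Without a tabulation by arm, a reader of the results could not tell whether this had occurred or in which direction.

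**Working it through.** **Inputs from section 9.** Alpha is 5%, with sidedness not given, and power is 80%. The assumed event rates are 30% in controls and 10% on bromhexine. The target is 118, or 59 per arm, and an assumed 15% dropout brings enrolment to 139.

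**Reproducing the plan's size.** Two proportions, unpooled variance, two-sided 5%:

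n = (1.960 + 0.842)² × (0.30 × 0.70 + 0.10 × 0.90) / 0.20² = 58.87, so 59 per arm.

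118 / (1 − 0.15) = 138.8, so 139.

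Both figures agree with the plan. Power at 59 per arm by the same formula is 80.1%. A pooled-variance formula gives 78.2%; that gap comes from the formula and has nothing to do with hydroxychloroquine. The unpooled formula is used below because it is the one that matches the plan.

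**Unequal use after entry.** Let u be the excess share of controls who start hydroxychloroquine early, and RR its risk ratio for the primary endpoint. Both are assumptions. The bromhexine rate is held at 10%.

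Control rate = 0.30 × (1 − u × (1 − RR))

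Power = Φ(difference / √[(p₁(1 − p₁) + p₂(1 − p₂)) / 59] − 1.960)

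| RR | u | Control rate | Difference (points) | Power |
|---|---|---|---|---|
| 1.0 | any | 30.0% | 20.0 | 80.1% |
| 0.8 | 10% | 29.4% | 19.4 | 78.0% |
| 0.8 | 40% | 27.6% | 17.6 | 70.9% |
| 0.65 | 20% | 27.9% | 17.9 | 72.2% |
| 0.5 | 10% | 28.5% | 18.5 | 74.6% |
| 0.5 | 30% | 25.5% | 15.5 | 61.4% |
| 0.5 | 40% | 24.0% | 14.0 | 54.0% |

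**The reverse case.** With 30% excess uptake on bromhexine at RR 0.5, the bromhexine rate is 0.10 × (1 − 0.3 × 0.5) = 8.5%. The difference widens to 21.5 points, which overstates bromhexine.

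**Leaving the factor out of the analysis.** This was checked by simulation with 60 per arm, two equal balanced strata and assumed control rates of 50% and 10%, which average the plan's 30%. With no treatment effect, a nominal 5% test rejects in about 3.1% of trials unadjusted and 5.1% with Mantel-Haenszel stratification. With the risk cut to one third, as in the plan, power is about 82% and 85%. The 50% v 10% split is a strong assumption; a weaker factor gains less.

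**Events available for adjustment.** 59 × 0.30 + 59 × 0.10 = 17.7 + 5.9 = 23.6, about 24. The full cross of four age bands, two zones and two hydroxychloroquine levels has 16 cells, or about 1.5 events per cell.

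**The case against.** The strongest objection is that the loss is conjecture. No section says how common hydroxychloroquine was, whether controls could obtain it, or whether anyone switched. The calculation places all the excess in one arm, and it applies the reduction to the whole 30% although those already taking the drug at entry cannot start it. At the modest end the loss is about 2 points. This stands: the figures show what unequal use could do and do not predict it.

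Four stronger readings are tempting, and the documents do not support them.

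- A reader might infer that the plan lets participants start or stop hydroxychloroquine freely. That comes from silence: no section permits it and none controls it.
- A reader might infer that minimising on hydroxychloroquine presumes that it protects. It presumes only that use may be prognostic, in either direction; users could simply be the more exposed staff.
- A reader might conclude that the design specifically masks a bromhexine effect. Masking needs both a protective drug and more uptake in controls, and the documents establish neither. If side effects were mistaken for COVID-19 and controls used more of the drug, suspected cases among controls would rise and bromhexine would look better. No section describes such side effects.
- A reader might think that hydroxychloroquine was singled out for neglect. Age and contact zone have no place in an analysis either, because none is described.

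It is also fair to say that the data are already being collected. The gap is in their use. A general analysis section added later could still omit prophylaxis taken after entry, so the point needs its own sentence.

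**Conclusion.** The concern holds as a gap in analysis and reporting. The plan balances a factor that it never analyses, and keeps a record that it never uses to show whether the arms stayed comparable on that factor.

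For unequal later use, the size is conditional. Power falls from 80% to about 78-54% over 10-40% excess uptake in controls and risk ratios of 0.8-0.5. The loss is nil at a risk ratio of 1, and the bias is in bromhexine's favour if the excess is on that arm. None of these inputs comes from the documents. The plan has no margin to absorb a loss, since 59 per arm is the minimum for 80% power and the 15% inflation covers dropout only.

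The case for analysing by the allocation factors does not depend on later use. It restores the nominal error rate if the factors are prognostic and costs little if they are not.

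**What to change.** 1. State that the primary combined endpoint is analysed as randomised, stratified (for example Mantel-Haenszel) or adjusted for the minimisation factors as entered at allocation: hydroxychloroquine, contact zone and age. Merge sparse age bands in advance, because about 24 events cannot support 16 cells.
2. From the existing Table 1 record, tabulate hydroxychloroquine starts and stops by arm, with dates. Word the conclusion as the effect of bromhexine added to the background prophylaxis actually taken, which is what an as-randomised comparison estimates.
3. State that use after randomisation is neither a covariate in the primary analysis nor a reason to exclude participants. It may be affected by allocation, and conditioning on it could introduce bias.

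An analysis censored at a change in prophylaxis is not needed. In particular, one based on time to positive PCR would test a secondary endpoint, so disagreement with the primary result could reflect the endpoint alone. If such an analysis is wanted, run it as exploratory on the primary combined endpoint and state that censoring may be informative, since exposure or early symptoms could prompt a start.

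The cost is a few sentences of analysis text, one table, and start and stop dates on a record already kept. The fix adds no visits or participants and does not change anyone's treatment.

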- 5. Peptic ulcer or duodenal ulcer, incl. in anamnesis

6. Documented contact with a SARS-CoV-2 carrier or a COVID-19 patient within 14 days prior to randomization

6. Drop out criteria

1. Failure to comply with the rules for the use of personal protective equipment when working with SARS-CoV-2 infection (the rules for the use of PPE in accordance with the recommendations of the Ministry of Health of Russia and internal orders of the General Director of the V.A. research; control of the use of PPE - independent);

2. Any acute illness not associated with SARS-CoV-2 that occurred during the study period

[figure not shown]
7. Study design

[figure not shown]
This is single-center study. Location of the study center:

Almazov National Medical Research Centre; [name]

Study design is present on Figure 1.

• When COVID-19 is expected clinically or SARS-CoV-2 infection is verified with a positive PCR test, the endpoint is reached and the drug may be canceled;

• However, the drug can be continued at the request of the participant for mild and moderate forms of the disease, since, theoretically, a decrease in viral load is possible; patients with continued therapy will continue to be followed, but outside the study protocol.

The same test systems for PCR (SARS-CoV-2 infection) will be used during the study.

8. Study endpoints

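### Bromhexine side effects are a criterion for withdrawing the participant, not only for stopping the drug, so primary outcomes can be lost from the bromhexine arm alone

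*Combined protocol and SAP*

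**What the plan says.** Section 12 is headed Subject exclusion. It begins with the participant's right to leave the study and adds "A participant might be excluded from the study for a medical emergency". It then introduces a list as "Study participant specific withdrawal criteria". The first entry is "The presence of side effects of the use of Bromhexine hydrochloride, which complicates its further safe use", extended to any other intolerance to the drug. The remaining entries are pregnancy, "Suspected / confirmed SARS-CoV-2 infection", and disability or hospitalisation related to that infection. Section 13 follows with "Participants excluded from the study will not be replaced".

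Four other places bear on how the list should be read:

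- Section 7, on a participant with clinical or PCR evidence of infection: "the endpoint is reached and the drug may be canceled".
- Section 8.3, item 8: "Additional observation of all study participants up to 8 weeks from the date of randomization".
- Section 10 has the drug, not the participant, stopped for renal or hepatic impairment. It does not say what follow-up comes afterwards.
- Section 9 inflates the sample from 118 to 139 for "Estimated dropout rate from study protocol (dropout after randomization, non-SARS-CoV-2 incidence) 15" per cent.

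The text defines no analysis population and no rule for missing outcomes.

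**The concern.** Stopping a drug and leaving a trial are different events, and Section 12 does not separate them. A participant who stops the tablets because of nausea can still be swabbed weekly and can still reach the primary endpoint. If that person is withdrawn, the outcome is lost. Control participants receive no study bromhexine, so they have no corresponding route out. The other entries on the list can occur in either arm.

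Losing outcomes from one arm for a reason tied to treatment means the remaining groups are no longer those formed by randomisation. The loss could also be related to the endpoint. Section 1 lists fever and bronchospasm among bromhexine's side effects, and clinical suspicion of COVID-19 counts towards the primary endpoint. In an unblinded trial, early symptoms in a treated participant could be put down to the drug and lead to withdrawal before a swab settles the question. This mechanism is inferred; the protocol does not describe it.

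**Working it through.** **1. The plan's own figures.** With 30% v 10%, two-sided 5% alpha (sidedness assumed), 80% power and unpooled variance:
n = (1.960 + 0.842)² × (0.30×0.70 + 0.10×0.90) / 0.20² = 58.9, so 59 per arm and 118 in total. Then 118 / 0.85 = 138.8, so 139. Both reproduce, and this point changes neither.

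**2. The text, side by side.**
- *For leaving the study:* the heading of Section 12, its two opening sentences and the wording of Section 13. Sections 7 and 10 also show that the authors write of stopping the drug when they mean that.
- *For stopping the drug only:* infection is on the same list, yet it is the primary event and Section 7 counts it. Section 8.3 item 8 times observation from randomisation, not from last dose.
- *Not settled:* whether someone withdrawn under Section 12 is still one of the participants in item 8.

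**3. Possible bias if withdrawn people are removed from the analysis.** All withdrawal rates are assumptions. Take 69 per arm, a true rate of 30% in both arms, and a two-sided 5% pooled z-test evaluated by exact binomial enumeration. Let w be the share of the bromhexine arm withdrawn and f the share of those who are true events. The observed bromhexine rate is (0.30 − w×f)/(1 − w). For w = 10% and f = 50% this is 0.25/0.90 = 27.8%. The chance of a significant result favouring bromhexine is 2.5% with no withdrawals. Otherwise:

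| f | w = 2% | w = 5% | w = 10% |
|---|---|---|---|
| 50% | 2.9% | 3.4% | 4.7% |
| 30% (unrelated to infection) | 2.5% | 2.5% | 2.5% |
| 0% | 2.1% | 1.6% | 0.9% |

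The bias can run either way, and it vanishes when withdrawal is unrelated to infection. That last result requires removal from the denominator. If people withdrawn before any event were instead counted as event-free, w = 10% at average risk would give 0.30 − 0.10×0.30 = 27% against 30%. The plan does not say which handling applies.

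**4. Worst-case bound.** Take control 21/69 and bromhexine 7 events, close to the planned rates.
- Five bromhexine outcomes lost: 7/64 v 21/69. Pooled rate 28/133 = 0.2105, SE 0.0708, z = 0.1950/0.0708 = 2.76, p = 0.006.
- All five were events: 12/69 v 21/69. Pooled rate 33/138 = 0.2391, SE 0.0726, z = 0.1304/0.0726 = 1.80, p = 0.07.
- Four lost, all events: 11/69 v 21/69, p = 0.044, still significant.

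If risks were independent, five events out of five would have probability 0.30⁵ = 0.0024 at 30% risk and 0.10⁵ = 0.00001 at 10%.

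**5. Power cost of keeping people in.** As an upper limit, everyone who stops does so at day 0 and takes the control risk. The bromhexine rate becomes 0.10 + 0.20×w.

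| w | Bromhexine rate | Power, 59 per arm | Power, 69 per arm |
|---|---|---|---|
| 0% | 10.0% | 80.5% | 85.7% |
| 2% | 10.4% | 78.5% | 83.8% |
| 5% | 11.0% | 75.2% | 80.9% |
| 10% | 12.0% | 69.5% | 75.5% |

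The column for 59 per arm is the relevant one, because the plan expects about 139 − 118 = 21 dropouts. For comparison, removing the same people when withdrawal is unrelated to infection gives 85.2%, 84.6% and 83.5% from 69 per arm.

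**The case against.** The strongest reply is that this is an ambiguity and not a shown loss of data. Being on the Section 12 list cannot by itself mean the outcome is discarded, since the primary event is on that list too. Item 8 can be read as covering everyone randomised. This stands, and it is why the point is conditional. It does not dispose of the point: losing someone after the primary event costs no primary outcome, whereas losing someone for intolerance in the first week does, and nothing expressly keeps that person in.

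Three stronger readings are tempting, and the documents support none of them:

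- *That the rule favours bromhexine.* This needs those withdrawn to have more than average infection risk. The documents give no figure for that, and an f of 50% is only an illustration.
- *That the 15% allowance shows the plan expects side-effect losses.* Section 9 does not name side effects. Its reference to illness other than SARS-CoV-2 matches the Section 6 drop-out criterion, which can occur in either arm.
- *That the five-outcome example predicts the result.* It is an extreme bound, and under independent risks a very unlikely one.

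It is also fair to say that Section 1 describes the side effects as minor, so withdrawals may be few. It calls nausea common, however, and gives no rate of stopping.

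**Conclusion.** The point holds in conditional form. Section 12, read with Section 13, makes drug intolerance a ground for withdrawing the participant, and because no placebo is described only the bromhexine arm can meet it. Applied as worded, this can remove primary outcomes from one arm after randomisation. A drug-stop reading remains open, and the documents do not show that outcomes will be lost, how many, or in which direction. Over assumed withdrawal of 2% to 10%, with those people removed from the analysis, the chance of a false benefit ranges from 0.9% to 4.7% against 2.5%. It is worth fixing because the remedy needs no new procedure; confidence is medium.

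**What to change.** In Section 12, make side effects and intolerance reasons to stop bromhexine only, and pregnancy likewise for consistency, although it is not specific to one arm. State that these participants continue the Table 1 PCR tests and clinical follow-up to week 8 unless they withdraw consent, and that they are analysed in their assigned arm. State in Section 8.3 item 8 that observation includes people who have stopped the drug. State also that suspected or confirmed infection is counted as the primary event and is not a withdrawal. If the sponsor always intended a drug stop, this only records it.

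The change is to wording; the swabs and visits are already scheduled. Its price is dilution from off-drug follow-up, bounded by the power figures above. The true loss is smaller, because people take some drug before they stop. If the sponsor expects stopping near 10%, the sample size should be reconsidered.

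### Section 7 puts follow-up of infected participants who stay on bromhexine off protocol, against the 8-week observation of everyone in 8.3; Section 12 adds to the conflict

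*Combined protocol and SAP*

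**What the plan says.** Section 7 covers what happens at infection. On clinical suspicion or a positive PCR, "the endpoint is reached and the drug may be canceled". It then adds that "the drug can be continued at the request of the participant for mild and moderate forms of the disease", and that those who do so are followed off protocol. It gives no follow-up rule for infected controls or for bromhexine participants who stop.

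Section 12 is headed as subject exclusion. Under "Study participant specific withdrawal criteria" it lists drug intolerance ("The presence of side effects of the use of Bromhexine hydrochloride, which complicates its further safe use"), pregnancy, and two infection items: "Suspected / confirmed SARS-CoV-2 infection" and "Period of disability and / or hospitalization associated with SARS-CoV-2 infection". Section 13 follows with "Participants excluded from the study will not be replaced".

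Other sections plan for observation after infection:

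- Section 8.2 counts symptomatic cases in both groups, counts COVID-19 by severity grade, and records bromhexine side effects.
- Section 8.3 items 3, 5 and 6 list CT, oximetry, severity laboratory tests, and the durations of oxygen and ventilator support. Item 8 has all participants observed to 8 weeks from randomization.
- Table 1 runs clinical follow-up and PCR through weeks 5 to 8, with no exception for infected participants.

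**The concern.** The severity grades in 8.2 can come only from infected participants, and severity is known only once the illness has run its course. A rule that takes some of these people off protocol at diagnosis fixes their grade at the trigger and not at its worst.

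The Section 7 rule can operate in one arm only, because controls have no bromhexine to continue. It also depends on the participant's choice in an open-label trial. If it is followed, a bromhexine participant who continues the drug and later worsens could stay in the count as mild or moderate, while a control with the same course is observed to 8 weeks. Any such error would understate severity in the bromhexine arm. Side effects in people still taking the drug would also fall off protocol. A suspected case who is PCR-negative or untested at the trigger, and positive later, could be missing from the symptomatic-case count.

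Section 12 widens the doubt to both arms. If its infection items end participation, the people who supply the severity data leave the study at the point when those data begin.

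**Working it through.** **The plan's own figure.** Section 9 assumes 30% and 10% incidence, 80% power and 5% alpha. Two-sided, with unpooled variance:

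n per arm = (1.96 + 0.8416)² × (0.3×0.7 + 0.1×0.9) / 0.2² = 58.87, rounded up to 59, so 118 in total.

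With 15% dropout: 118 / 0.85 = 138.8, so 139. The stated figures reproduce and nothing here changes them.

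**Reach of the Section 7 sentence** (59 per arm, plan rates)

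- Bromhexine: 59 × 0.10 = 5.9 reach the endpoint. This is a ceiling at that rate, because severe disease and those who do not ask to continue fall outside the sentence.
- Control: 0.
- The ceiling depends on the assumed effect. If bromhexine did nothing and its arm also ran at 30%, it would be 59 × 0.30 = 17.7.

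**Reach of the Section 12 infection items, read literally**

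- Control: 59 × 0.30 = 17.7. Bromhexine: 59 × 0.10 = 5.9. Total: 23.6 of 118, or 20%.
- Section 9 cites 20% to 50% incidence in medical personnel, though not for this composite endpoint. With bromhexine held at 10% as an assumption, the low end is 59 × 0.20 + 5.9 = 17.7 of 118 (15%). The high end is 59 × 0.50 + 5.9 = 35.4 of 118 (30%).

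These are numbers of people to whom a rule could apply. The documents give no basis for the share whose later symptoms, worsening or PCR result would go unrecorded, so none is estimated.

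**The texts compared**

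- Section 7 against 8.3 item 8: the first takes a named subgroup off protocol, the second observes everyone to 8 weeks. They conflict whatever Section 12 means.
- Section 12 against 8.2, 8.3 and Table 1: they conflict if withdrawal means leaving the study, and agree if it means stopping the drug.
- Primary endpoint (8.1): suspicion or a positive PCR is itself the event, so it is already recorded when either rule takes effect.

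**The case against.** The best defence is that most of the text supports the drug-stop reading of Section 12, and that much of this is a drafting matter.

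- That reading makes every item in 8.3 and Table 1 workable; the other defeats several of them.
- The first Section 12 item is drug intolerance. The hospitalization item would be largely redundant if infection had already ended participation, and its reference to a period suggests an interruption.
- Section 6 limits illness-related dropout to "Any acute illness not associated with SARS-CoV-2 that occurred during the study period", and the 15% allowance in Section 9 likewise names non-SARS-CoV-2 illness. With 20% expected to reach the endpoint, the planners evidently did not count infected participants as dropouts.
- Section 13 only bars replacement and is silent on observation.
- Figure 1 is not shown and may settle the matter.
- Unscheduled hospitalization is a reportable SAE under 15.2, which gives another route for capturing severe cases.

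Most of this stands for Section 12. Some doubt remains. Where the protocol means stopping the drug, as in Sections 7 and 10, it says so, and Section 12 does not. A drug-stop rule also has no content for controls, who make up 17.7 of the 23.6 exposed. The SAE route helps only while the person still counts as a study subject.

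The defence does not reach the Section 7 sentence. No other visible text cancels it, and reading Section 12 as drug stop leaves it in place. Section 7 does say that these participants continue to be followed, so the information may exist, but it would sit off protocol.

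A reader might infer that the plan discards outcomes for a fifth of its participants, or that the primary comparison is biased. The documents support neither. The 20% is exposure under a reading that most of the text disfavours, and the primary event precedes any withdrawal.

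**Conclusion.** The point holds as a minor one. The firm part is Section 7: a stated rule that contradicts 8.3 item 8 and can act only in the bromhexine arm, on at most about 5.9 of 59 participants at the plan's rates. If followed, it makes the severity and symptomatic-case counts in 8.2 less complete in one arm than in the other.

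The weaker part is Section 12, which is ambiguous and more likely means stopping the drug. About 23.6 of 118 participants would be exposed under the literal reading, with no loss established. If 8.3 item 8 governs, nothing is lost beyond what the Section 7 sentence causes.

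This rests on the plan's incidence assumptions and on the visible text, Figure 1 being unavailable. The primary endpoint, sample size and PCR schedule are unaffected.

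**What to change.** Section 7: state that bromhexine continued after infection is treatment outside the protocol, but that outcome observation of these participants stays within it.

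Section 12: make the two infection items reasons to stop the study drug only. Add that reaching the primary endpoint does not end participation, and that in both arms symptom, severity and safety observation continues to 8 weeks under 8.3 item 8. PCR stays as Table 1 already schedules it for those not yet confirmed.

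Cost: wording changes in two sections and slightly more recording in infected participants, which 8.3 and Table 1 already plan. No added participants or tests, and no change to the primary endpoint.
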